the radial artery will be identified by palpation, and the cannula will be directed by continuous or intermittent palpation of arterial pulsation. The attending anesthesiologist will supervise the resident and act as the second operator if needed. An attempt is defined as a new penetration of the skin with the needle, followed by an unlimited number of subcutaneous needle redirections. Clinical judgment by the supervising anesthesiologist is used to determine the time allowed for an attempt, number of attempts allowed, and changes to a new site. The attending anesthesiologist will take over arterial cannulation if residents perform for more than 3 times or > 15 minutes. The start time is defined when the operator's finger is initially placed on the patient's wrist. The end point for both methods is when the arterial catheter is successfully placed. Primary outcome is first-attempt success rate, and secondary outcomes comprise time to successful arterial catheterization, number of attempts, sites and catheters used. Complications related to arterial cannulation will also be recorded, including pain, hematoma formation, and arterial vasospasm or occlusion.

Substudy 3. Comparing the effectiveness of preoxygenation between HFNC and facemask: A single-blind randomized controlled trial

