Patients will be randomized in an allocation ratio of 1:1 into HFNC group (N=40) or facemask group (N=40). Preoxygenation will be performed according to the randomization group for a 5-minute duration. In the HFNC group, preoxygenation will be performed using HFNC (Optiflow™, Fisher & Paykel Healthcare, Auckland, NZ), nasal prongs set at 30 L/min flow of heated and humidified 100% oxygen. In the facemask group, patients will breath spontaneously with an anesthetic facemask and 100% oxygen 15 L/min.⁶¹ Gas flow for HFNC or facemask can be adjusted depending on patients' tolerance. After preoxygenation, general anesthesia will be induced with propofol 1.5 – 2.0 mg/kg ideal body weight, alfentanil 8 – 10 µg/kg total body weight, and rocuronium 0.8 – 1.0 mg/kg ideal body weight. Rapid sequence intubation will be performed in all patients. During laryngoscopy intubation, HFNC will be left in place with the nasal flow escalated to 50 L/min of 100% oxygen in order to achieve apneic oxygenation. In the facemask group, the facemask will be removed when apnea occurs. After tracheal intubation, correct placement of the endotracheal tube will be confirmed by capnography and the nasal prongs of the HFNC group will be removed. If desaturation (SpO₂ < 92%) occurs, patients will be then administered 100% O₂, and the recruitment maneuver (peak airway pressure 40 cm H₂O for 10 seconds) will be applied until SpO₂ restores to baseline values. Primary outcome is PaO₂ after preoxygenation. Secondary outcomes are SpO₂ before preoxygenation, after preoxygenation, and after intubation, desaturation event (SpO₂ < 92%), the lowest SpO₂ during intubation, PaO₂ before preoxygenation, and PaCO₂ before and after preoxygenation, alveolar-arterial oxygen gradient (A-a gradient)⁶², and patient comfort levels. All the outcomes will be measured by a nursing anesthetist, blinded to group allocation. Arterial line will be placed before induction. Arterial blood gas will be measured twice: first, before the preoxygenation in room air and, second, just after the 5-minute preoxygenation. Comfort levels of the HFNC and standard facemask will be assessed using a 10-point Likert scale, and patients will be asked which of the two devices they preferred regarding comfort before referral to ward.

Substudy 4. The effect of type of volatile anesthetics and M-Entropy guidance of anesthesia depth on postoperative recovery: A double-blind randomized controlled trial

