The distributions of baseline patient characteristics and outcome variables will be compared between two groups using chi-square tests or Fisher's exact test for categorical variables and either t tests or Wilcoxon rank sum tests for continuous variables, as appropriate. For four-group comparisons, either ANOVA tests or Kruskal-Wallis tests will be used for continuous variables, as appropriate. A Bonferroni correction to the significance criterion for multiple comparisons is applied where appropriate. For time to event data, Kaplan-Meier method and log-rank test will be applied for group comparisons. Multivariable logistic regression, simple linear regression, or Cox proportional hazards regression analyses will be used to identify potential influential factors of outcomes of interest. A two-sided significance level of 0.05 was used to define statistically significant difference. All the statistical analyses will be conducted using Statistics Analysis System (SAS), Version 9.4 (SAS Institute Inc., Cary, NC, USA).

According to prior study³⁷, at least 37 patients in each group of HFNC or facemask preoxygenation are needed to detect a difference of 30 seconds of nonhypoxic apnea time between the HFNC and facemask group, accepting a type I error of 5% and type II error of 20% with anticipated nonhypoxic apnea time of mean $188 \pm SD 46$ seconds in the facemask group.⁶⁵ Nevertheless, in order to allocate 20 patients into each group of volatile anesthesia with desflurane or sevoflurane with or without M-Entropy guidance, a total of 80 patients will be enrolled in this study.

TMU-JIRB Form059/20180201
Protocol Number: N202002076
Version : 4
Date : 2020.04.08

There are about 120 patients undergoing LSG at our hospital per year. Considering the patient selection criteria and possible patient refusal, a total of 50 patients per year will be enrolled in this study. Therefore, it will take about 2 years for patient recruitment. Besides, the investigators will select all randomized subjects for analysis.

Reference

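### Substudy 3 lists three pre-device measurements as secondary outcomes, and no planned treatment comparison uses the room-air blood gas as a baseline

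*Combined protocol and SAP*

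**What the plan says.** All references are to the combined protocol and SAP, version 4.

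- **Substudy 3, outcomes.** The primary outcome is PaO₂ after preoxygenation. On the secondary outcomes the text reads "Secondary outcomes are SpO₂ before preoxygenation, after preoxygenation, and after intubation", and later in the same list "the lowest SpO₂ during intubation, PaO₂ before preoxygenation, and PaCO₂ before and after preoxygenation".
- **Substudy 3, blood gases.** Two arterial samples are planned, with no restriction to a subgroup: "first, before the preoxygenation in room air and, second, just after the 5-minute preoxygenation". On arterial access it says "Arterial line will be placed before induction".
- **Substudy 2, cannulation.** "The attending anesthesiologist will take over arterial cannulation if residents perform for more than 3 times or > 15 minutes".
- **Statistical Analysis Plan, group comparisons.** "The distributions of baseline patient characteristics and outcome variables will be compared between two groups", with "either t tests or Wilcoxon rank sum tests for continuous variables, as appropriate". Bonferroni correction is applied where judged appropriate, without a defined family.
- **Statistical Analysis Plan, regression.** Multivariable logistic regression is named, then "simple linear regression, or Cox proportional hazards regression analyses will be used to identify potential influential factors of outcomes of interest". No covariate is named. The section ends by saying that all randomised subjects will be analysed.

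**The concern.** A value taken before the device is applied cannot depend on which device was assigned. Any difference between arms in SpO₂, PaO₂ or PaCO₂ before preoxygenation is chance. Listing these values as secondary outcomes mixes results that can answer the Substudy 3 question with results that cannot.

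Relabelling them would not by itself stop the testing, because the same SAP sentence also tests baseline characteristics between groups.

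Meanwhile the room-air PaO₂, the natural covariate for the primary outcome, enters no planned estimate of the device effect. The planned comparisons are unadjusted. The regressions are there to look for influential factors, and a linear model with one predictor cannot hold both arm and baseline PaO₂. What is at stake is a clear outcome list and a possibly narrower confidence interval, not the validity of the comparison.

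**Working it through.** **1. The plan's own figure.** The SAP sizes the comparison on nonhypoxic apnea time: difference 30 s, SD 46 s, two-sided 5%, 80% power. n = 2 × [46 × 2.8016 / 30]² = 36.9, so 37 per group, as stated; 40 per arm are enrolled. That variable is not among the Substudy 3 outcomes and the documents give no SD for PaO₂, so what follows is in SD units of PaO₂.

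**2. Pre-device outcomes.** Three true-null tests at 0.05 give 1 − 0.95³ = 14.3% chance of at least one false positive, if independent. I count ten secondary outcomes. Bonferroni over all ten would give 0.05/10 = 0.0050; without the three pre-device values, 0.05/7 = 0.0071.

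**3. Unadjusted primary comparison.** At 40 per arm, two-sided 5% and 80% power, the noncentral t (78 df) gives a detectable difference of 0.6343 SD. The normal approximation, 2.8016 × √(2/40), gives 0.626.

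**4. Adjusted for room-air PaO₂.** Let r be the correlation between room-air and post-preoxygenation PaO₂ (an assumption). The variance is multiplied by (1 − r²)(1 + 1/76), with 77 df.

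| r | Variance factor | CI width relative to unadjusted | Detectable difference (SD) | Power at 0.634 SD |
|---|---|---|---|---|
| 0 | 1.013 | 1.007 | 0.639 | 79.5% |
| 0.1 | 1.003 | 1.002 | 0.635 | 79.9% |
| 0.2 | 0.973 | 0.986 | 0.626 | 81.1% |
| 0.3 | 0.922 | 0.960 | 0.609 | 83.1% |
| 0.5 | 0.760 | 0.872 | 0.553 | 89.5% |

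The factor equals 1 when r² = 1/77, that is |r| = 0.114. On the detectable difference the break-even is 0.115.

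**5. Missing baselines (number assumed, equal per arm).** If patients without a room-air gas drop out of the model, 2 of 80 missing brings r = 0.2 back to 0.634 SD, and 6 of 80 brings r = 0.3 back to 0.634 SD. Filling with the mean pooled across arms replaces r² by r²(1 − k/80), where k is the number missing. This gives 0.626 and 0.611 SD, so nearly all the gain is kept. In simulation (20,000 trials per cell) the type I error with filling was 4.7–5.2%.

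**6. Shape of PaO₂ (assumed).** Power at 0.634 SD from 20,000 simulated trials per cell. The skewed shapes are negative lognormal scaled to SD 1, with r set on the underlying normal scale.

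| Shape | Adjusted linear model, r = 0.1 / 0.3 / 0.5 | Unadjusted Wilcoxon, same r |
|---|---|---|
| Normal | 80 / 83 / 89% | 78 / 78 / 77% |
| Mild left skew (log-SD 0.25, skewness −0.8) | 80 / 83 / 89% | 83 / 82 / 82% |
| Strong left skew (log-SD 0.5, skewness −1.75) | 80 / 82 / 88% | 92 / 92 / 92% |

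Across all nine cells the adjusted model kept a type I error of 4.7–5.2% and CI coverage of 94.8–95.3%.

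**The case against.** The case against has real substance.

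- **The gain may be small or nil.** The documents give no r. The baseline is on room air and the outcome on 100% oxygen, gas flow may be adjusted to tolerance, and the Eligible Criteria exclude room-air SpO₂ below 90%, which restricts the range. All of this points to a low r. This stands; the gain is possible, not assured.
- **The Wilcoxon test, already allowed, can be the stronger test.** This stands for strong left skew, at every r examined. It is the price of a prespecified mean difference with a confidence interval, and a reason to keep Wilcoxon as a named analysis.
- **With normal data the fair comparator is the t test.** Correct. The like-for-like gain is the one in step 4: 80% to 83% at r = 0.3, and none at r = 0.1.
- **Some planned analysis might use the first gas.** The alveolar-arterial gradient has no stated time point, and the multivariable logistic model could include baseline PaO₂. But a room-air gradient would only be a further pre-device measure, and the logistic model names no covariates and is for factor-finding. Neither adjusts the device effect on PaO₂.
- **Missing baselines are conjecture.** The documents do not show that any will be missing; taking the first gas as planned already requires a line in place before preoxygenation. But the separate sentence on the line says only that it precedes induction, and cannulation can be prolonged. A filling rule is a harmless safeguard, not evidence of a defect.

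**Conclusion.** The concern holds. That three pre-device values are listed as secondary outcomes, and that no planned treatment comparison adjusts for the room-air gas, follows from the text with no assumption.

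The size of the precision loss is uncertain. It ranges from nothing (|r| below about 0.11–0.12) to a confidence interval 1.4% wider than it need be relative to the unadjusted width at r = 0.2, 4.0% at r = 0.3 and 12.8% at r = 0.5. These figures assume 40 per arm with complete data; r, the number of missing baselines and the shape of PaO₂ are all assumed. The planned unadjusted test is valid under randomisation, so there is no bias and the trial is not invalidated. The change is worth making because it is cheap.

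**What to change.** **Substudy 3.** Move SpO₂, PaO₂ and PaCO₂ before preoxygenation from the secondary outcomes to the baseline characteristics.

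**Statistical Analysis Plan.**
- State that baseline characteristics are described by arm without significance tests.
- Prespecify the primary Substudy 3 analysis as a linear model of untransformed PaO₂ after preoxygenation on arm and room-air PaO₂, reporting the adjusted difference with its 95% CI.
- Keep every randomised patient who has an outcome by filling a missing room-air PaO₂ with the mean pooled across arms, and report the number filled per arm.
- Name the unadjusted Wilcoxon test in advance as the sensitivity analysis.
- Analyse PaCO₂ after preoxygenation in the same way, with its own baseline.

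**Cost.** A small wording change in two sections and no new measurement, since both gases are already planned. The downsides are an interval about 0.7% wider if r is near zero, and lower power than Wilcoxon if PaO₂ is strongly left-skewed (about 80–82% against 92% at r = 0.1 to 0.3 under the assumed shape). The filling rule covers a missing baseline only; a patient with no gas after preoxygenation is a separate missing-outcome question.

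### Substudy 3 claims blinded measurement of every outcome but gives no means of blinding for SpO2 during preoxygenation and intubation, and comfort cannot be blinded

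*Combined protocol and SAP*

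**What the plan says.** The heading of Substudy 3 reads "Comparing the effectiveness of preoxygenation between HFNC and facemask: A single-blind randomized controlled trial" and does not say who is blinded. The only statement on the subject in the text is: "All the outcomes will be measured by a nursing anesthetist, blinded to group allocation". It makes no exception for any outcome.

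The outcomes it covers are:
- **Primary:** PaO2 after preoxygenation.
- **Secondary:** SpO2 before preoxygenation, after preoxygenation and after intubation; the desaturation event (SpO2 < 92%); the lowest SpO2 during intubation; PaO2 before preoxygenation; PaCO2 before and after; the A-a gradient; and patient comfort.

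On the devices, the same section says "During laryngoscopy intubation, HFNC will be left in place with the nasal flow escalated to 50 L/min of 100% oxygen". For the other arm: "In the facemask group, the facemask will be removed when apnea occurs". Once tube placement is confirmed, "the nasal prongs of the HFNC group will be removed". On comfort: "Comfort levels of the HFNC and standard facemask will be assessed using a 10-point Likert scale". Patients are also asked which device they preferred.

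**The concern.** Patients are awake for preoxygenation and the team applies the device, so blinding of the outcome assessor is the only blinding the substudy offers. The statement claims it for every outcome, while the procedure leaves the allocated device in view for part of the measurement period.

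Two consequences follow. First, if a person reads a changing SpO2 display while aware of the arm, brief dips could be noted more readily in one arm than in the other. The lowest SpO2 and the < 92% event carry the aim, stated in the Introduction, of assessing HFNC in preventing desaturation. Second, the protocol commits to CONSORT, so the report will have to say who was blinded and how. Following the present text, it would describe patient-rated comfort, and SpO2 read beside a visible device, as blinded.

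**Working it through.** **Step 1. Set each outcome against the procedure.**

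| Outcome | What can be seen or known when it is measured | Can the blinding statement hold as written? |
|---|---|---|
| SpO2 before preoxygenation | Precedes the 5-minute preoxygenation in both arms | Yes |
| PaO2 and PaCO2 before and after; A-a gradient | No masking is described at sampling, but the values come from blood gas analysis | Little room for assessor bias |
| SpO2 after preoxygenation | End of the 5 minutes on prongs or mask | Hard to reconcile; no mechanism given |
| Lowest SpO2 during intubation | Prongs on at 50 L/min, or mask removed | Hard to reconcile; no mechanism given |
| SpO2 < 92% event | No window is stated; in the intubation window, as above | Hard to reconcile in that window |
| SpO2 after intubation | Prongs come off after intubation; exact timing of the reading is not stated | Possibly |
| Comfort and device preference | The patient is the rater and was awake with the device | No, wherever the nurse is placed |

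**Step 2. Look for a mechanism.** Substudy 3 mentions no screen, remote display, stored trend or separate location for the assessor. It also gives no source, sampling interval or window for the lowest SpO2 or the event. Mechanisms are described elsewhere: Substudy 1 uses a second anesthesiologist blinded to the preoperative evaluation, and Substudy 4 conceals the Entropy number and EEG waveform in the usual care group.

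**Step 3. Sensitivity of the < 92% comparison.** The plan gives no figure on this point. Its one calculated sample size, 37 per group, concerns nonhypoxic apnea time and has no bearing here.

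Inputs from the plan: 40 patients per arm (Substudy 3); two-sided 0.05 and chi-square or Fisher's exact test (Statistical Analysis Plan). Assumed inputs: a true event rate p equal in both arms, and a fraction m of events unrecorded in one arm only.

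The recorded rates are then p and p(1 − m). With a and b events recorded in the two arms,

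false-positive rate = Σₐ Σ_b Bin(a; 40, p) × Bin(b; 40, p(1 − m)) × [test significant at 0.05].

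For the uncorrected chi-square test, with t = a + b, the table is significant when 80 × [a(40 − b) − b(40 − a)]² / [40 × 40 × t × (80 − t)] exceeds 3.84.

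Example: with p = 0.30 and m = 0.25, the recorded rates are 0.30 and 0.30 × 0.75 = 0.225, and the chi-square rate is 11.7%. With m = 0.50 they are 0.30 and 0.15, and it is 36.6%.

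| True rate p | Test | None missed | Quarter missed in one arm | Half missed in one arm |
|---|---|---|---|---|
| 10% | Chi-square | 5.9% | 7.8% | 14.6% |
| 10% | Fisher | 1.7% | 2.1% | 4.3% |
| 20% | Chi-square | 5.1% | 9.2% | 24.7% |
| 20% | Fisher | 2.8% | 5.5% | 16.2% |
| 30% | Chi-square | 4.8% | 11.7% | 36.6% |
| 30% | Fisher | 2.8% | 7.8% | 28.1% |
| 40% | Chi-square | 5.2% | 15.2% | 49.7% |
| 40% | Fisher | 3.0% | 10.5% | 40.8% |

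If only a tenth of events are missed at p = 30%, the chi-square rate is 5.9%. At p = 10% the expected count is at most 40 × 0.10 = 4 events per arm, where Fisher's test would normally be chosen, so the Fisher row is the relevant one there.

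**The case against.** The strongest reply is that the documents do not say where the nursing anesthetist stands or how SpO2 is captured. A reading from a screened monitor or a stored record could be blinded. A reader might infer that blinding does not exist for SpO2, or that it can hold only for the blood gases. The text supports neither. The defensible statement is that blinding is asserted without a mechanism and is hard to square with the procedure. SpO2 before preoxygenation, and possibly SpO2 after intubation, can be read with no device showing.

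A reader might also infer that the comfort questions reveal the arm to the nurse. They need not: they name both devices and are asked before referral to the ward. A nurse could record the answers while blinded. The difficulty is that the rating is the patient's.

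It is also fair to say that SpO2 is an instrument reading with a fixed cut-off, that the affected outcomes are secondary, and that a fall below 92% triggers 100% oxygen and a recruitment maneuver, so most events should leave a clinical trace. Losing half the events in one arm is therefore hard to credit, and the upper end of the range is not a forecast. This limits the probable bias in SpO2. It does not rescue a blinding claim covering every outcome, because comfort contradicts it outright and the SpO2 claim cannot be verified from the text.

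**Conclusion.** The blinding statement is too broad. For SpO2 after preoxygenation, the lowest SpO2 during intubation and < 92% events in that window, it lacks a mechanism and sits badly with the described procedure. For comfort and device preference it cannot apply. The primary outcome, the other blood gas values and SpO2 before preoxygenation are not materially affected, and nothing here calls the primary comparison into question.

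The size is unknown. Over the assumed range in the table (event rates of 10% to 40%, a quarter to a half of events missed in one arm), the false-positive rate for the event comparison runs from 2.1% (Fisher, 10%, quarter missed) to 49.7% (chi-square, 40%, half missed). The result depends on the assumed rates and on the test chosen. It covers the binary event only, not the lowest SpO2 or comfort. The correction is still worth making: it is cheap and protects the outcomes that address desaturation.

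**What to change.** 1. Take SpO2 after preoxygenation, SpO2 after intubation, the lowest SpO2 and the < 92% event from the monitor's stored, time-stamped record, using fixed windows set in advance. First confirm that the monitor can export SpO2; the documents do not say so.
2. Have the values extracted from files coded by study number, by a member of the existing team who did not attend that induction or by an automatic rule. Coding alone does not re-blind someone who was in the room.
3. If this is not possible, describe these SpO2 outcomes as unblinded.
4. Limit the blinding statement to blood gases and record-derived SpO2, and say who is blinded under the single-blind label.
5. Report comfort and device preference as unblinded, patient-reported outcomes.

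The cost is data-export work, arranging for an extractor who was not at the induction, and a change of wording. Treatment, sample size and visits stay as they are.

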Patients will be randomized by a computer-generated list into one of the four groups, desflurane with usual care (N=20), desflurane with M-Entropy guidance (N=20), sevoflurane with usual care (N=20), and sevoflurane with M-Entropy guidance (N=20). At the operating room, a M-Entropy™ sensor and S/5™ module (GE Healthcare, Helsinki, Finland) will be applied to all patients' forehead before induction of anesthesia according to the manufacturer's recommendations. This will be connected to a M-Entropy Monitor that will be concealed from the patients and operators.

In the M-Entropy group, dosage of volatile anesthetics will be adjusted to achieve the Response and State Entropy value between 40 and 60 from the start of anesthesia to the end of surgery. In the usual care group, dosage of volatile anesthetics will be titrated according to clinical judgment. This will be to maintain arterial pressure within 20% range of the baseline and the heart rate within the range 50 to 100 beats/min. In case of signs of inadequate anesthesia (e.g. movement, cough and swallowing), anesthetic dose will be increased. M-Entropy monitoring will be continued in the usual care group, but the Entropy number and EEG waveform will be concealed from the anesthetist in charge. Entropy values, hemodynamic, and expiratory gas data will be recorded in 5-min intervals. In all patients, cessation of general anesthesia will be timed to facilitate early awakening after wound closure. All patients will be decurarized from rocuronium-induced neuromuscular blockade with sugammadex dosed at 2 mg/kg ideal body weight + 40%.⁶³ Primary outcome is time to spontaneous eye opening. Secondary outcomes include time to tracheal extubation, time to orientation in time and place, and time to leave operating room, event of emergence agitation. The Richmond Agitation-Sedation Scale (RASS) will be used to evaluate the level of agitation and sedation promptly after extubation.⁶⁴ For patients who are transferred to the intensive care unit for postoperative mechanical ventilation, the investigators will record the time to extubation.

Statistical Analysis Plan

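### Substudy 3 sets no pre-induction time for the comfort score: the only time given for any comfort question falls after anesthesia and surgery

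*Combined protocol and SAP*

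**What the plan says.** All of the relevant text is in the Study Protocol, under Substudies 3 and 4.

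- **Exposure.** Each patient has one allocated device: "Preoxygenation will be performed according to the randomization group for a 5-minute duration".
- **Outcome.** Comfort closes the list of secondary outcomes: "alveolar-arterial oxygen gradient (A-a gradient)⁶², and patient comfort levels". The primary outcome is PaO₂ after preoxygenation.
- **Instrument.** "Comfort levels of the HFNC and standard facemask will be assessed using a 10-point Likert scale". This clause gives no time.
- **Time.** The second half of the same sentence has patients asked "which of the two devices they preferred regarding comfort before referral to ward". No other time for a comfort question appears anywhere.
- **What comes in between.** "After preoxygenation, general anesthesia will be induced with propofol", together with an opioid and a neuromuscular blocker. Intubation, volatile anesthesia and sleeve gastrectomy follow. The volatile agent and the use of entropy guidance are allocated separately in Substudy 4: "Patients will be randomized by a computer-generated list into one of the four groups".
- **Contrast.** Substudy 3 ties its second arterial blood gas to the end of the five-minute period. Comfort has no such anchor.

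**The concern.** The experience to be rated is short, awake and finished before the first induction drug. A rating given on the far side of an anesthetic, a tracheal tube and abdominal surgery depends on memory of those five minutes. It may also reflect residual sedation, throat discomfort or pain. Answers that do not depend on the device pull the two arms together, so a real difference could be missed, or a null result could be read as equal comfort.

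This matters because comfort belongs to the rationale. The Background section on preoxygenation strategy says HFNC may be more comfortable than facemask ventilation. A score not collected before induction cannot be recovered later.

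**Working it through.** **1. The two readings of the sentence**

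| Reading | When the 10-point score is taken | Consequence |
|---|---|---|
| The time phrase governs both clauses | After anesthesia, surgery and the Substudy 4 treatment | A recall measure in every patient |
| The time phrase governs only the preference clause | Not stated | Could be before induction in some patients and after surgery in others |

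The grammar favors the second reading and nothing in the text excludes the first. Neither secures a score taken while the experience is current.

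**2. The plan's own figure**

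The only sample-size calculation is in the Statistical Analysis Plan and concerns nonhypoxic apnea time: difference 30 s, SD 46 s, two-sided 5%, power 80%.

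n per group = 2 × [46 × (1.960 + 0.842) / 30]² = 36.9, rounded up to 37. This agrees with the stated 37. It says nothing about comfort, for which the documents give no SD, target difference or recall rate.

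**3. What 40 per arm can detect for comfort, in SD units**

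Detectable difference at 80% power = (1.960 + 0.842) × √(2/40) = 0.63 SD.

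**4. Illustrations on assumed inputs (normal approximation, power = Φ[d√(n/2) − 1.96])**

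*Dilution.* Suppose a share m of patients answer independently of the device and the SD is unchanged. The expected difference is then (1 − m) times the true one.

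| Assumed m | True 2 points appears as | Power for a true 0.63 SD |
|---|---|---|
| 0 | 2.0 | 80% |
| 0.25 | 1.5 | Φ(0.75 × 2.80 − 1.96) = 56% |
| 0.50 | 1.0 | Φ(0.50 × 2.80 − 1.96) = 29% |

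*Random recall error.* With reliability r, the standardized difference is multiplied by √r. Assumed r of 0.9, 0.7 and 0.5 gives power of 76%, 65% and 51%.

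*Missing ratings.* With 4 or 8 assumed missing per arm, the detectable difference rises from 0.63 SD to 2.80 × √(2/36) = 0.66 or 2.80 × √(2/32) = 0.70 SD.

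These figures show direction and scale only. The values of m, r and the number missing, and the 2-point difference, are assumptions.

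**5. Patients ventilated in intensive care**

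Substudy 4 foresees such patients and plans to record their time to extubation. It does not say whether or when they are asked about comfort. The Statistical Analysis Plan analyzes all randomized subjects and has no rule for a missing rating.

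**The case against.** **The time phrase belongs to the preference question.** This stands as grammar. A reader might infer that the protocol schedules the 10-point score after surgery, or immediately before transfer. The text says neither. What remains is an outcome with no fixed time, which the same sentence of repair would cure.

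**Substudy 4 does not bias the device comparison.** This also stands. It is tempting to say that rating comfort after a second randomized treatment confounds the result. That treatment is allocated separately, so it is balanced in expectation between HFNC and facemask. It can add noise, chance imbalance or effect modification, but not systematic bias. The agitation scale does not show otherwise: "The Richmond Agitation-Sedation Scale (RASS) will be used to evaluate the level of agitation and sedation promptly after extubation" describes an earlier moment than ward referral.

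**Ventilated patients could still answer.** Agreed. A reader might conclude that their ratings cannot be obtained, but the plan expects extubation, after which they could be asked before reaching a ward. Their ratings would be delayed and possibly missing. The documents give no number of such patients.

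**Nothing shows that patients forget.** The exposure precedes every listed induction drug and no sedative premedication is described. This is why the attenuation is presented only as a possibility.

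**Scoring with the device in place reveals the allocation.** This is a real cost, but a small one. The nursing anesthetist described as blinded is assigned all outcomes, including the lowest SpO₂ during intubation, when the nasal cannula stays on and the facemask has been removed. The comfort rating comes from the patient, who knows the device in any case.

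**Conclusion.** The point holds in a limited form. The plan contains no pre-induction comfort rating, and the one time it gives for a comfort question falls after anesthesia, surgery and the Substudy 4 treatment. The 10-point score is thus either post-anesthesia recall or a measure taken at no fixed time.

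Recall error and post-operative state would add noise and could shrink a true difference. The documents give no basis for stating by how much, and the figures above depend wholly on assumed recall. The effect is confined to comfort as a secondary outcome. PaO₂, PaCO₂, SpO₂ and desaturation are untouched, and no sample-size figure changes. The change is worth making because it is cheap and the lost information cannot be restored, not because the substudy's main conclusion is at risk.

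**What to change.** In Substudy 3, state that the 10-point comfort score for the allocated device is taken at the end of the five-minute preoxygenation, at the time of the second arterial blood gas and before any induction drug. The patient can show the number by finger or on a card. If a score before ward transfer is also kept, label it as recall and do not base the device comparison on it. State how a missing rating is handled, including for patients who go to intensive care for ventilation.

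The cost is a sentence or two in the protocol and one line on the case report form. It also takes a few seconds before induction, and the person recording the score sees the device, as the planned measurements during intubation already entail. No extra visit, procedure or patient is needed.
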